The relationship between changes from baseline in QTc at specified time points post-dose and plasma concentrations of LANRA may be assessed. A separate plan for such analyses will be generated in accordance with principles outlined in International Council for Harmonisation (ICH) Directive E14 with results reported separately from the main clinical study report for this trial. Other exposure-response relationships (efficacy, safety and biomarkers) may be conducted, if supported by sufficient data.

Best response (CR, CRh, complete remission with incomplete blood count recovery [CRi], partial response [PR], stable disease [SD], and progressive disease [PD]) will be summarized for the efficacy-evaluable population by frequency distributions and percentages in accordance with ELN 2017 criteria ([Appendix 2](#)). Patients with no post-baseline response assessments will be considered non-responders. The 80% confidence intervals (CIs) for estimates of the proportion of patients with CR/CRh will be constructed with exact methods for the binomial distribution (eg, Clopper-Pearson intervals). Additionally, 80% CIs for estimates of the proportion of patients with any CR (CR, CRh, CRi) will be constructed in a similar manner.

EFS is defined as the time from C1D1 until treatment failure (ie, failure to achieve CR or CRh), relapse from CR/CRh or death from any cause. DOR is defined as the time from the first documented CR/CRh until relapse or death. Kaplan-Meier (KM) methodology will be used to estimate the medians for EFS and duration of response and at specified landmark

CONFIDENTIAL

Protocol KB-LANRA-1001 v7.0 Global  
(Amendment 6.0 Global)

timepoints. The 80% CIs for estimates of the medians and landmark rates for EFS and duration of response will be calculated using log-log transformation. Duration of follow-up will be estimated using the reverse KM method. Patients who do not experience the event of interest will be censored at the last assessment of response at which they were both alive and relapse-free. All summaries of EFS and those for duration of response will employ the safety and efficacy evaluable populations, respectively. OS will be estimated using KM methodology. Patients alive at last follow-up will be censored at the date of last contact.

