### 2.2.1 Gilteritinib:

Gilteritinib is a small-molecule, oral FLT3 inhibitor with highly specific and potent inhibition of FLT3 receptors with both ITD and D835 mutations (either alone or in combination) (Mori et al, 2017; Lee et al, 2017). *In vivo*, gilteritinib inhibited tumor growth and induced tumor regressions in mice xenografted with MV4-11 AML cells (Mori et al,

2017). A Phase 1/2 dose-escalation/expansion study (the CHRYSALIS study) evaluated the safety/tolerability, pharmacokinetic (PK), and antileukemic activity of once-daily gilteritinib as a single agent at doses of 20–450 mg in patients with R/R, *FLT3*-wild type (n=58) or *FLT3*-mutated AML (n=194) (James et al, 2020; Perl et al, 2017). Gilteritinib was well tolerated with a maximally tolerated dose (MTD) of 300 mg QD. Potent *FLT3* inhibition and dose-proportional PK were observed across all doses. Doses  $\geq$  80 mg/day were associated with  $>$  90% *FLT3* inhibition and an overall response rate of 52% (including 41% with CR, CRi [CR with incomplete blood count recovery] or CRp [CR with partial platelet count recovery]) among patients with *FLT3*-mutated disease (Perl et al, 2017) and a median OS of 31 weeks. The Phase 3 ADMIRAL trial compared the efficacy and safety of gilteritinib as a QD dose of 120 mg with standard, either high or low intensity, salvage chemotherapy in patients with *FLT3*-mutated, R/R AML. The median OS in the gilteritinib treated group was 9.3 months vs. 5.6 months for the chemotherapy-treated group (HR, 0.64; 95% CI, 0.49 to 0.83;  $P < 0.001$ ) (Perl et al, 2019). Thirty-four percent of patients achieved CR with full or partial hematologic recovery in the gilteritinib group compared with 15.3% in the chemotherapy group; the percentages of patients achieving CR were 21.1% and 10.5%, respectively. Grade  $\geq$ 3 adverse events (AEs) and serious adverse events (SAEs) occurred less frequently in the gilteritinib group than in the chemotherapy groups when adjusted for therapy duration. The most common Grade  $\geq$ 3 AEs in the gilteritinib group were febrile neutropenia (45.9%), anemia (40.7%), and thrombocytopenia (22.8%) (Perl et al, 2019). Results from the CHRYSALIS and ADMIRAL studies were the basis for the recent FDA and EMA approval of gilteritinib in patients with R/R, *FLT3*-mutated AML.

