## **14.0 Criteria for Study Discontinuation**

Study participation will be discontinued for the following reasons:

- Death
- Withdrawal of consent
- Trial is discontinued by the study sponsor

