### 15.2.10 Efficacy Analyses

Best response (CR, CRh, CRi, partial response [PR], stable disease [SD], and progressive disease [PD]) will be summarized for the efficacy-evaluable population by frequency distributions and percentages in accordance with ELN criteria ([Appendix 2](#)). Patients with no post-baseline response assessments will be considered non-responders. The 80% CIs for estimates of the proportion of patients with CR/CRh will be constructed with exact methods for the binomial distribution (eg, Clopper-Pearson intervals). Additionally, 80% CIs for the estimates of the proportion of patients with any CR (CR, CRh or CRi) will be constructed in a similar manner.

EFS is defined as the time from C1D1 until treatment failure (ie, failure to achieve CR or CRh), relapse from CR/CRh or death from any cause. DOR is defined as the time from the first documented CR/CRh until relapse or death. Kaplan-Meier (KM) methodology will be used to estimate the medians for EFS and duration of response and at specified landmark timepoints. The 80% CIs for estimates of the medians and landmark rates for EFS and duration of response will be calculated using the log-log transformation ([Kalbfleisch and Prentice, 1980](#)). Duration of follow-up will be estimated using the reverse KM method. Patients who do not experience the event of interest will be censored at the last assessment at which they are deemed relapse-free. All summaries of EFS and duration of response will employ the safety and efficacy evaluable populations, respectively. OS will be estimated using KM methodology. Patients alive at last follow-up will be censored at the date of last contact.

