The sum of the LANRA doses administered to a patient measured in milligrams (mg)

Cumulative Dose of Gilteritinib

The sum of the gilteritinib doses administered to a patient measured in milligrams (mg)

Actual Dose Intensity of LANRA (mg/cycle)

Defined as the cumulative dose of LANRA / (duration of exposure / 28)

Actual Dose Intensity of Gilteritinib (mg/cycle)

Defined as the cumulative dose of gilteritinib / (duration of exposure / 28)

Relative LANRA Dose Intensity

Relative dose is set to $100 * (\text{Actual LANRA Dose Intensity} / \text{Expected Cumulative Dose} / 28)$

Relative Gilteritinib Dose Intensity

Relative dose is set to $100 * (\text{Actual Gilteritinib Dose Intensity} / \text{Expected Cumulative Dose} / 28)$

Treatment Interruptions

Treatment Interruptions will be defined as doses that are missed for any reason and will be calculated using the Dosing Log eCRF page by obtaining the number of missed doses over the duration of treatment.

Dose Reductions

Dose reductions will be defined as a planned reduction in dose level for AE management. These will be managed as noted in Table 2 (for gilteritinib) and Table 3 (for LANRA) of the protocol and identified by comparing the dose received as recorded in the Dosing Log eCRF page versus the dose assigned.

Duration of Follow-up

Duration of follow-up will be defined as the End of Study date – C1D1 + 1. End of study date is collected on the End of Study eCRF. Patients who are lost to follow-up will be censored at their date of last contact.

Measurable Residual Disease (MRD)

Presence of leukemia cells using a molecular characterization platform (eg. RT-PCR, NGS)

MRD Negative

A patient is considered MRD Negative if he/she has exhibits MRD negativity (<0.01%) in bone marrow as measured by a molecular assay for *FLT3* mutation (e.g., by next generation sequencing) in a central laboratory in the setting of a CR or CRh .

Overall Survival

The time from enrolment until death from any cause.

Complete Remission (CR)

Complete remission requires all of the following:

- Bone marrow blasts <5%
- Absence of circulating blasts and blasts with Auer rods
- Absence of extramedullary disease (ie. leukemia outside of bone marrow confirmed by biopsy)
- Absolute neutrophil count > 1.0 x 10⁹/L (1,000/μL)
- Platelet count > 100 x 10⁹/L (100,000/μL)

Complete Remission with partial hematologic recovery (CRh)

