- Grade 4 neutropenia or thrombocytopenia lasting > 28 days after treatment onset that is not attributed to active AML and at least possibly related to LANRA.

- Any toxicity resulting in reduction in the dose of LANRA in Cycle 1.

*In general, infection will not constitute a DLT unless it is assessed as having resulted from unexpectedly prolonged myelosuppression in the setting of < 5% blasts in the bone marrow, absence of myelodysplastic changes, and/or absence of AML by flow cytometry in the bone marrow.

Adverse Event

An AE is defined as any unfavorable or unintended sign, symptom, laboratory abnormality or disease (new or exacerbated) temporally associated with the use of a study drug, whether considered causally related to the study drug or not.

All AEs defined as reportable in Section 16.6 of the protocol will be recorded on the ADVERSE EVENTS CRF.

Treatment-emergent Adverse Event (TEAE)

Any adverse event that occurs on or after C1D1 and up to the End-of-Treatment visit following discontinuation of the last study drug is considered treatment-emergent.

Events that occur after the initiation of non-protocol anti-leukemic therapy will be considered as non-treatment emergent even if they occur before the End-of-Treatment visit.

Treatment-emergent Laboratory Toxicity (TELT)

A TELT is identified based on the laboratory data recorded in the eCRF and is defined as a National Cancer Institute - Common Toxicity Criteria for Adverse Events (NCI-CTCAE) v5.0 (NCI 2017) grade 1 or higher abnormality, which occurs on or after C1D1 and up to the End-of-Treatment visit and exhibits at least 1 grade shift from the baseline value.

Events that occur after the initiation of non-protocol anti-leukemic therapy will be considered as non-treatment emergent even if they occur before the End-of-Treatment visit.

Concomitant Medications

Concomitant medications are those medications taken on or after C1D1. This includes medications started prior to C1D1 and continued after C1D1. These medications will be recorded in the PRIOR/CONCOMITANT MEDICATION eCRF.

Prior Medications

Prior medications are those medications taken from the time of informed consent until C1D1. These medications will be recorded in the PRIOR/CONCOMITANT MEDICATION eCRF.

End of Study

After all enrolled patients either relapse or die or 5 years after the last patient enrolls (whichever is earlier) or if the sponsor decides to terminate the trial.

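### SAP 4.4.4 replaces the protocol's reverse Kaplan-Meier follow-up with time on study and censors losses, an undeclared change that would understate follow-up if the figure were reported

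*SAP*

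**What the plan says.** Protocol 15.2.10 states: "Duration of follow-up will be estimated using the reverse KM method". The Statistical Analysis part of the Synopsis names the same method.

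SAP 4.4.4 has a different rule under Duration of Follow-up: "Duration of follow-up will be defined as the End of Study date – C1D1 + 1". It gives the source of the date, "End of study date is collected on the End of Study eCRF", and then the censoring rule, "Patients who are lost to follow-up will be censored at their date of last contact". The entry names no estimator. Reverse Kaplan-Meier appears nowhere in the SAP text.

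Two other entries decide what the SAP date means. Protocol 14.0 begins "Study participation will be discontinued for the following reasons" and lists death, withdrawal of consent and discontinuation of the trial by the sponsor. SAP 4.4.4 also defines End of Study for the trial as a whole: "After all enrolled patients either relapse or die or 5 years after the last patient enrolls (whichever is earlier"), or when the sponsor terminates the trial.

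Overall survival runs from enrolment in both documents and is kept in SAP 6.5 and Table 14.2.2. SAP Section 7 records the move from 80% to 95% confidence intervals and the restriction to Phase 1b. It says nothing about follow-up.

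**The concern.** Median follow-up tells the reader how long patients were observed, or would have been had they not died, and so how mature the survival estimate is. Reverse Kaplan-Meier serves this purpose by censoring deaths and counting the end of observation while alive as the event. The SAP variable, read naturally, closes at death and censors losses. Its median then depends on mortality as much as on observation time. It would be short in a population with poor survival even if every patient were followed closely, and a dose group with more early deaths would look less well followed than one observed equally long.

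The trial stopped after Phase 1b, so a reader of the OS results has particular reason to ask how long patients were followed.

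**Working it through.** The documents give no follow-up figure to reproduce. The check compares the two rules by patient group and then sizes the difference under stated assumptions.

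**Rules by patient group**

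| Patient's last status | Protocol (reverse KM) | SAP 4.4.4, natural reading |
|---|---|---|
| Died | censored at death | completed time |
| Lost to follow-up | event at last contact | censored at last contact |
| Alive at study end | event | completed time |

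The first two rows are reversed and the third is the same.

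**Inputs**

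- Median OS *m* = 9.3 months, from Protocol 2.2.1: "The median OS in the gilteritinib treated group was 9.3 months vs. 5.6 months for the chemotherapy-treated group". This is one arm of another trial and is used only for illustration.
- Assumed, not in the documents: exponential survival; potential follow-up uniform from *a* to *b* months; 5% loss per year; censoring independent of survival.

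**Formulas**

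Let G(t) be the probability that potential follow-up exceeds t: 1 up to *a*, then (b − t)/(b − a).

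- SAP rule by Kaplan-Meier (deaths and study end as events, losses censored): curve = 2^(−t/m) × G(t).
- Reverse Kaplan-Meier (losses and study end as events, deaths censored): curve = 0.95^(t/12) × G(t).

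Because G(t) ≤ 1, the SAP curve never lies above the survival curve from C1D1, so its median cannot exceed median survival from that origin.

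**Potential follow-up of 6 to 24 months**

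- SAP rule at t = 7.85: 2^(−7.85/9.3) × (24 − 7.85)/18 = 0.557 × 0.897 = 0.500. The median is about 7.8 months.
- Reverse Kaplan-Meier at t = 14.43: 0.95^(14.43/12) × (24 − 14.43)/18 = 0.940 × 0.532 = 0.500. The median is about 14.4 months.
- Median potential follow-up: (6 + 24)/2 = 15 months.

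A simulation of 200,000 patients under the same assumptions gave 7.9 and 14.5 months.

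**Other ranges (same formulas, months)**

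| Potential follow-up | SAP rule | Reverse KM | Potential median |
|---|---|---|---|
| 3–18 | 6.1 | 10.2 | 10.5 |
| 6–24 | 7.8 | 14.4 | 15 |
| 6–30 | 8.1 | 17.1 | 18 |

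**Does the missing estimator matter?** A plain median of the SAP interval, without Kaplan-Meier, was simulated at 6.0, 7.6 and 7.8 months for the three ranges. The direction does not depend on the estimator.

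**Mature and short follow-up.** A separate simulation used median OS of 9.3 months and 10% yearly loss.

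- 24-month accrual plus 12 months: SAP rule 9.3 months, equal to median OS; reverse Kaplan-Meier 21.5.
- 18-month accrual with cut-off at the last patient in: 5.0 against 8.3.
- The first setting with 69 patients, the Phase 1b maximum: medians of 9.3 (5th to 95th percentile 6.9 to 12.2) against 21.6 (17.5 to 27.6).

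**Dependence on mortality.** With potential follow-up held at 6 to 24 months and median OS set to 5, 9.3 or 14 months (5 and 14 are assumed), the SAP rule gives 5.0, 7.8 and 9.6 months. Reverse Kaplan-Meier stays at 14.4.

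**The case against.** The strongest reply is that nothing planned uses this variable. SAP Section 6 has no follow-up summary, and Section 10 lists no table or listing of it. A reader might infer that the study report will carry a wrong median follow-up, by dose group. The documents do not support that, because no such output is scheduled. This stands and limits the importance of the point.

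Second, the SAP does not say that deaths are events. A reader might infer that it prescribes a Kaplan-Meier analysis opposite to the protocol's. It does not: it defines an interval, and the handling of deaths follows from the eCRF date together with Protocol 14.0. The sentence on losses could be loose wording that only supplies an end date. Even so, the text is not reverse Kaplan-Meier, and a programmer following it would not produce that estimate.

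Third, the trial-level End of Study definition sits in the same section. If that date were meant, the variable would be close to potential follow-up and would not be shortened by deaths. The eCRF sentence favours a patient-level date, but one term has two meanings and needs settling.

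Fourth, Protocol 15.0 lets the SAP modify planned analyses and requires an amendment only for major changes to the primary endpoint or its analysis. That is correct. The fault is that Section 7 does not record the change.

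Finally, a reader might infer that the SAP median always lands on median survival. It does so only once follow-up is mature; with short follow-up it falls below.

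**Conclusion.** The concern holds in a limited form. SAP 4.4.4 departs from the protocol's method without declaring it and, on the natural reading, handles deaths and losses the opposite way. A median from the variable cannot exceed median survival from C1D1, and it was below reverse Kaplan-Meier in every scenario run. In the main illustration it is about 7.8 against 14.4 months.

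The direction rests on the patient-level reading of the End of Study date. The months also rest on assumed accrual, potential follow-up, loss rates and exponential survival, and on an OS median from another trial. No endpoint estimate or primary analysis is affected. What is at stake is the description of OS maturity, if the report quotes follow-up at all. The correction is worth making but is not critical.

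**What to change.** In SAP 4.4.4 and 6.5, state that follow-up is estimated by reverse Kaplan-Meier from enrolment, the same origin as OS. The event is the last contact alive, whether through loss to follow-up, withdrawal or study end; deaths are censored at the date of death. State that any End of Study date used is the patient-level eCRF date, not the trial-level definition.

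Add the overall median with its 95% CI to Table 14.2.2. By-dose values should be descriptive only, since a 3 + 3 cohort without backfill may have only 3 to 6 evaluable patients.

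If the sponsor prefers time on study, Section 7 should declare and justify that choice, and the quantity should be labelled as time on study.

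The cost is a few sentences of SAP wording and one table line. No new data are needed beyond the survival status and contact dates already required for OS.

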### 3.0 Objectives & Endpoints:

#### 3.1 Phase 1b

Objectives:	Endpoints:
Primary:	
To evaluate the safety of LANRA in combination with the FLT3 inhibitor gilteritinib, in patients with R/R FLT3 -mutated AML.	Type, incidence, severity, causality, and outcome of AEs, including serious and Grade $\geq 3$ AEs; dose-limiting toxicities (DLTs); MTD/RP2D of LANRA in combination with standard doses of gilteritinib.
Secondary:	

To characterize the PK of LANRA alone and in combination with gilteritinib.
 
To characterize the PK of gilteritinib when administered in combination with LANRA.
 
To evaluate preliminary antileukemic activity of the combination in patients with R/R FLT3-mutated AML.
	
Standard PK parameters including (but not limited to) maximal plasma concentration (<math>C_{max}</math>), time to maximal plasma concentration (<math>T_{max}</math>) and area under the plasma concentration <math>\times</math> time curve from hour 0 to the last measurable time point (<math>AUC_{0-last}</math>).
 
Composite complete response (CR) rate including CR and CR with partial hematologic recovery (CRh) as defined by European LeukemiaNet (ELN) 2017 criteria (Döhner 2017).
 
Duration of response (DOR), defined as the time from first qualifying response (CR/CRh) until relapse or death from any cause, as assessed by study investigators.
 
EFS, defined at the time from treatment onset until treatment failure (ie, failure to achieve CR/CRh), relapse from CR/CRh, or death from any cause.
 
OS, defined as the time from enrollment until death from any cause.

Exploratory:	

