## 11.2 Confirmation of Eligibility

All screening assessments and relevant medical history must be available and reviewed by the investigator before eligibility can be confirmed. Eligibility waivers will not be granted. After the investigator determines that a patient is eligible, study site personnel will complete an enrollment authorization form to be sent to the medical monitor for review/approval. Written authorization by the medical monitor is required before a patient can be officially enrolled and begin study treatment.

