*** Certain targeted therapies, for example, those inhibiting mutant IDH proteins, other kinases or targets may cause a Differentiation Syndrome, i.e., a transient increase in the percentage of bone marrow blasts accompanied by an increase in circulating blasts. In the setting of therapy with such

compounds, an increase in blasts may not necessarily indicate progressive disease. Such instances should be discussed with the study medical monitor on a case-by-case basis.

Composite Complete Remission (cCR)

Achieving either complete remission or complete remission with partial hematologic recovery.

Duration of Response

Duration of response is defined as the time from first qualifying CR (CR or CRh) until relapse or death from any cause, as assessed by study investigators.

Event-free survival (EFS)

Event-free survival (EFS) is defined as the time from C1D1 until treatment failure (i.e., failure to achieve CR or CRh), relapse from CR/CRh or death from any cause.

Dose Limiting Toxicity

A DLT is defined as any of the following toxicities occurring within the DLT assessment period *unless it can be unequivocally determined to be unrelated to LANRA*:

- A nonhematologic toxicity of Grade ≥ 3 that is at least possibly related to LANRA with the exception of:
 - nausea, and vomiting controlled with antiemetic therapy,
(Note: Grade 3 nausea or vomiting that requires tube feeding, total parenteral nutrition and/or initial or prolonged hospitalization for management will constitute a DLT. Grade 4 nausea or vomiting will always constitute a DLT regardless of management.)
 - infection or infection-related toxicities such as fever/sepsis, febrile neutropenia*,
 - fatigue, alopecia,
 - isolated electrolyte abnormalities (ie. those without clinical consequences) correctable to Grade ≤ 1 within 72 hours with or without supplementation,
 - Grade 3 or 4 Differentiation Syndrome successfully managed with high-dose steroids plus supportive care interventions with resolution within 7 days and without resulting end-organ damage.
- Any toxicity resulting in administration of $< 80\%$ of the cumulative, Cycle 1 dose for either LANRA or gilteritinib.
 - Note: Administration of $< 80\%$ of the cumulative Cycle 1 dose for LANRA or gilteritinib for reasons other than toxicity (eg, non-compliance or administrative reasons) will not be considered a DLT but will make the subject unevaluable for purposes of MTD determination and require the subject to be replaced.

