5.2. SAFETY POPULATION

The Safety Population consists of all patients who receive ≥ 1 dose of either study drug and have at least 1 on-treatment safety-related observation, where a safety-related observation is defined as a reported AE or post-baseline assessment of vital signs, ECGs or safety laboratory assessments.

Patients will be analyzed according to their assigned dose level. The safety population will be used for all summaries of Safety data.

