10. PROPOSED TABLES, LISTINGS, AND FIGURES

Tables	
14.1.1	Subject Disposition and Discontinuation Summary, All Patients Enrolled: Phase 1b
14.1.2.1	Demographics, Safety Population : Phase 1b
14.1.2.2	Baseline Disease Characteristics, Safety Population : Phase 1b
14.1.4.1	Summary of Exposure, Safety Population: Phase 1b
14.1.4.2	Summary of Prior Antileukemic Regimens, Safety Population: Phase 1b
14.2.1	Summary of Best Response by ELN 2017 response criteria, Efficacy Evaluable Population: Phase 1b
14.2.2	Overall Survival, Safety Population: Phase 1b
14.3.1.1	Overview of Treatment Emergent Adverse Events, Safety Population: Phase 1b
14.3.1.2	Treatment-Emergent Adverse Events by System Organ Class, Preferred Term (All Cycles), Safety Population: Phase 1b
14.3.1.3	Treatment-Emergent Non-Serious Adverse Events by System Organ Class, Preferred Term (All Cycles), Safety Population: Phase 1b
14.3.1.4	Grade 3 or 4 Treatment-Emergent Adverse Events by System Organ Class, Preferred Term and Greatest Severity (All Cycles), Safety Population: Phase 1b
14.3.1.5	Treatment-Emergent Serious Adverse Events by System Organ Class, Preferred Term (All Cycles), Safety Population: Phase 1b
14.3.1.6	Treatment Related Adverse Events by System Organ Class, Preferred Term (All Cycles), Safety Population: Phase 1b

14.3.1.7	Treatment Emergent Adverse Events Leading to Dose Reduction by System Organ Class, Preferred Term (All Cycles), Safety Population: Phase 1b
14.3.1.8	Treatment Emergent Adverse Events Leading to Treatment Discontinuation by System Organ Class, Preferred Term (All Cycles), Safety Population: Phase 1b
14.3.1.9	Treatment Emergent Adverse Events Leading to Death by System Organ Class, Preferred Term (All Cycles), Safety Population: Phase 1b
14.3.2	Select Grade 3 or 4 Treatment-Emergent Laboratory Toxicities, All Cycles, Safety Population: Phase 1b
14.3.3	Electrocardiogram by Worst QTcF Results: Phase 1b
Listings	
16.2.1	Subject Disposition, All Patients Enrolled: Phase 1b
16.2.2.1	Informed Consent, All Patients Enrolled: Phase 1b
16.2.2.2	Subject Eligibility, All Patients Enrolled: Phase 1b
16.2.3	Analysis Populations, All Patients Enrolled: Phase 1b
16.2.4.1	Demographics, All Patients Enrolled: Phase 1b
16.2.4.2	General Medical History, All Patients Enrolled: Phase 1b
16.2.4.3	AML Diagnosis, All Patients Enrolled: Phase 1b
16.2.4.4	Additional AML Details, All Patients Enrolled: Phase 1b
16.2.4.5	Prior Systemic Anti-Leukemia Regimens, All Patients Enrolled: Phase 1b

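### Overall survival is timed from enrolment but tabulated only in dosed patients, so any wait between enrolment and first dose counts as guaranteed survival

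*SAP*

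**What the plan says.** **Origin.** Protocol Section 3.1 gives "OS, defined as the time from enrollment until death from any cause". SAP Section 4.4.4 uses the same origin: "The time from enrolment until death from any cause".

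**Population.** SAP Section 10 titles Table 14.2.2 "Overall Survival, Safety Population: Phase 1b". SAP Section 5.2 defines that set: "The Safety Population consists of all patients who receive ≥ 1 dose of either study drug and have at least 1 on-treatment safety-related observation". SAP Section 6.5, which describes the OS analysis, names no population. SAP Section 5.5 makes the Efficacy Evaluable set the default for efficacy summaries unless another is stated, and that set also requires a dose. All Patients Enrolled exists as a separate set. It is used for the disposition table (14.1.1) and for the listings, but not for OS.

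**Method.** SAP Section 6.5 plans Kaplan-Meier with 95% confidence intervals for the quartiles and censoring at last contact. It mentions neither left truncation nor a landmark.

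**Order of events.** Protocol Section 11.2 says: "Written authorization by the medical monitor is required before a patient can be officially enrolled and begin study treatment". Neither document says which date counts as the enrolment date, and neither sets a minimum or maximum interval from enrolment to first dose.

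**The concern.** The clock starts at one event and entry to the table depends on a later one. A patient enrolled on day 0 and dosed on day 7 is in the table only because they survived those 7 days, yet the 7 days count as observed survival. A patient who was enrolled and died on day 5 without a dose is not in the table at all. This is immortal time, and a plain Kaplan-Meier estimate does not remove it.

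What is at stake is the accuracy of the only time-to-event table in SAP Section 10. A reader is likely to set its median beside published survival figures, including the 9.3 months for gilteritinib and 5.6 months for chemotherapy that protocol Section 2.2.1 cites from the randomised Phase 3 trial.

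**Working it through.** The documents give no OS median, event count or power, so there is no figure of the plan's own to reproduce. The check has two parts.

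**1. Direction**

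- Against a C1D1 clock, the same dosed patients each have their own gap added to their time. The gap cannot be negative, so no time gets shorter.
- Against all enrolled patients timed from enrolment, suppose that only death prevents dosing. Beyond the longest gap, the planned curve is S(t) divided by the probability of surviving the gap. That is never below S(t).

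**2. Size**

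Inputs:

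- Medians M = 9.3 and 5.6 months (protocol Section 2.2.1), used only to set a scale.
- Gap g = 0 to 21 days, **assumed**. Protocol Section 6.1 requires screening to be completed within 21 days before treatment, and enrolment follows screening, so 21 days is an implied ceiling.
- Up to 69 Phase 1b patients (SAP Section 4.2).
- One month = 30.4375 days.

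Model: exponential survival from enrolment with hazard h = ln 2 / M. Among patients alive at dosing, S(t) = exp(-h(t - g)) for t > g. Setting this to 0.5 gives a median of M + g. The probability of dying in the gap is 1 - exp(-hg).

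Example, M = 9.3 months = 283 days and g = 21 days:

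- h = 0.693 / 283 = 0.00245 per day
- shift = 21 / 30.4375 = 0.69 month, and 0.69 / 9.3 = 7.4%
- probability of dying in the gap = 1 - exp(-0.0514) = 5.0%, or 0.0501 × 69 = 3.5 patients

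| Gap (days) | Shift (months) | Median, M = 9.3 | Median, M = 5.6 | Die in gap, M = 9.3 | Die in gap, M = 5.6 |
|---|---|---|---|---|---|
| 0 | 0 | 9.30 | 5.60 | 0% | 0% |
| 1 | 0.03 | 9.33 (+0.4%) | 5.63 (+0.6%) | 0.2% | 0.4% |
| 3 | 0.10 | 9.40 (+1.1%) | 5.70 (+1.8%) | 0.7% | 1.2% |
| 7 | 0.23 | 9.53 (+2.5%) | 5.83 (+4.1%) | 1.7% | 2.8% |
| 14 | 0.46 | 9.76 (+4.9%) | 6.06 (+8.2%) | 3.4% | 5.5% |
| 21 | 0.69 | 9.99 (+7.4%) | 6.29 (+12.3%) | 5.0% | 8.2% |

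At 21 days, 12-month survival would read 0.430 instead of 0.409 (M = 9.3) or 0.247 instead of 0.226 (M = 5.6).

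A fixed 21-day gap for everyone is the extreme. A simulation with gaps spread uniformly (2,000,000 draws per setting) gives these medians in months:

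| Gap | M | Dosed, from enrolment | Dosed, from C1D1 | All enrolled, from enrolment |
|---|---|---|---|---|
| 0-7 days | 9.3 | 9.41 | 9.29 | 9.29 |
| 0-21 days | 9.3 | 9.65 | 9.31 | 9.31 |
| 0-7 days | 5.6 | 5.71 | 5.60 | 5.60 |
| 0-21 days | 5.6 | 5.95 | 5.60 | 5.60 |

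Both consistent pairings of origin and population recover the true median up to simulation error. Only the planned pairing does not.

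**The case against.** **The gap may be very short.** The 21-day period begins at consent (protocol Section 11.1), and enrolment comes only after screening results have been reviewed and the medical monitor has approved. What remains of the window may be a few days or nothing. This stands: 21 days is a ceiling, not a typical value.

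**Sampling error is larger.** With exponential survival and every patient dying, the 95% interval for a median is about exp(±1.96/√n). That is -21% to +27% at n = 69 and -35% to +55% at n = 20, the cohort maximum. This also stands, but it does not excuse an avoidable bias in a known direction.

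**Exclusions would be visible.** Table 14.1.1 covers all enrolled patients, and survival status and deaths are listed for them. A pre-dose death could be found there, but the OS estimate would not change.

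**The enrolment origin is the protocol's own.** True, which is why a move to C1D1 must be recorded as a departure.

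A reader might also infer more than the documents support:

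- *That every OS time contains such a stretch.* No minimum gap is set, and enrolment and dosing on the same day is compatible with protocol Section 11.2.
- *That the on-treatment observation adds further immortal time.* SAP Section 5.2 says "a safety-related observation is defined as a reported AE or post-baseline assessment of vital signs, ECGs or safety laboratory assessments". Any reported adverse event qualifies, and Phase 1b schedules ECGs from 1 hour after the C1D1 dose, so this condition adds almost nothing.
- *That OS conflicts with EFS or follow-up results reported beside it.* SAP Section 4.4.4 does say "Event-free survival (EFS) is defined as the time from C1D1 until treatment failure", and starts duration of follow-up at C1D1 too. But SAP Section 6.5 sets out no EFS analysis, and Section 10 lists no EFS table and no table naming duration of follow-up.
- *That dose levels will appear to differ in survival.* This needs gaps that vary by cohort, and nothing in the documents shows that.
- *That a planned comparison with gilteritinib alone is compromised.* No OS comparison with 9.3 months is planned. The external benchmark in SAP Section 4.2 is for CR/CRh in Phase 2, which was not enrolled.

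**Conclusion.** The mismatch between origin and population is real and can bias reported OS only upward or not at all. It holds whether the Safety Population or the Efficacy Evaluable default applies, because both require a dose.

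The size depends on a gap that the documents do not state. It is zero if enrolment and first dose fall on the same day, about 0.1 to 0.2 month for an assumed 3 to 7 days, and about 0.7 month at the 21-day ceiling. These figures rest on exponential survival and on death being the only reason an enrolled patient goes undosed.

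SAP Section 4.1 states that there is no formal hypothesis and that the analysis is descriptive. No error rate, power or decision rule is affected. The point is minor, but worth correcting because the correction is so cheap.

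**What to change.** Choose one consistent pairing:

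1. **C1D1 origin, dosed patients.** In SAP Section 4.4.4, define OS as date of death (or last contact) - C1D1 + 1. Keep the Safety Population for Table 14.2.2, and record the departure from the protocol definition in SAP Section 7.
2. **Enrolment origin, all enrolled.** Keep the protocol definition, run Table 14.2.2 on All Patients Enrolled, and state which date counts as enrolment.

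Under either option, name the OS population in SAP Section 6.5, so that the Section 5.5 default and the title of Table 14.2.2 cannot be read as disagreeing.

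The cost is one start date or one population label in the program, plus a line or two of SAP text. No new data are needed, since survival status is already to be listed for all enrolled patients. The only downside is that reported OS may come out a few days shorter.
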